#### **9.4.11. Follow-up of AEs and SAEs**

After the initial AE/SAE report, the Investigator is required to proactively follow each participant at subsequent visits/contacts. All SAEs will be followed until resolution, stabilization, the event is otherwise explained, or the participant is lost to follow-up (as defined in Section 8.4).

#### **9.4.12. Disease-related Events or Disease-related Outcomes Not Qualifying as AEs or SAEs**

##### **9.4.12.1. Adverse Events that are Vaso-Occlusive Crisis Events**

VOC events are not reported as an AE/SAE and must be reported on the VOC page.

If the underlying cause of an SAE is determined to be a VOC, then the SAE will be entered on the VOC page and not reported as an SAE.

If the underlying cause of an SAE is determined not to be a VOC, then the SAE must be recorded in the SAE page and reported as an SAE.

The following disease-related events are common in participants with SCD, independent of exposure to study intervention, can be serious/life-threatening, and are defined as endpoints in this protocol:

- Uncomplicated VOC (defined as an acute episode of pain with no medically determined cause other than a vaso-occlusive event, results in a visit to a medical facility (hospitalization, emergency department, urgent care center, outpatient clinic, or infusion center), and requires parenteral narcotic agents, parenteral nonsteroidal anti-inflammatory drugs (NSAIDs), or an increase in treatment with oral narcotics, but is NOT classified as an acute chest syndrome, hepatic sequestration, splenic sequestration, dactylitis, or priapism.)
- Complicated VOC:
  - Acute chest syndrome
  - Hepatic sequestration
  - Splenic sequestration
  - Priapism requiring a visit to a medical facility
  - Dactylitis

Because these events are typically associated with the disease under study, they will not be reported according to the standard process for expedited reporting of SAEs even though the event may meet the definition of an SAE. These events will be recorded on the VOC page in the participant's CRF within 72 hours. These disease-related events will be monitored by an independent data monitoring committee and safety review team on a routine basis.

Note: However, if either of the following conditions applies, then the event must be recorded and reported as an SAE (instead of disease-related events):

- The event is, in the investigator's opinion, of greater intensity, frequency, or duration than expected for the individual participant.

OR

- The investigator considers that there is a reasonable possibility that the event was related to study intervention.

#### **9.4.12.1.1. Procedures for Reporting and Documenting VOC Event Data**

All VOCs, as defined in Section 9.4.12.1, are to be documented within the eCRF within 5 days of a site becoming aware of such event. Each VOC is to be recorded only once on the "Vaso-Occlusive Event" eCRF page. All VOCs are to be recorded throughout the entire treatment period, up to Week 48, and should continue until the Follow-Up Visit at Week 60 for participants who do not enroll in the OLE study (or earlier if participant discontinues from the study). The Investigator will classify and provide all the following information for each VOC as follows:

- Diagnosis, which will be limited to one of the pre-defined VOC events as described in Section 9.4.12.1:
  - Uncomplicated VOCs
  - Acute chest syndrome
  - Hepatic sequestration
  - Splenic sequestration
  - Priapism (requiring a visit to a medical facility)
  - Dactylitis
- Onset date,
- Stop date,
- Action taken (none, required concomitant medication, temporarily withheld study drug, permanent discontinuation of study drug, or other [explain]),
- Whether or not hospitalization or a visit to emergency department, urgent care center, outpatient clinic, or infusion center was required,
- Concomitant medications given, and
- Outcome (recovered without sequelae, resolved with sequelae, ongoing, unknown, death).

If a participant is hospitalized due to a VOC and during hospitalization develops a non-VOC event that meets the criteria for a SAE, then that event should be reported as a SAE. Any prolongation of a hospitalization due to a non-VOC event (even though they may have initially been hospitalized due to a VOC) is reportable as a SAE in the eCRF.

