**Study Arms:**

Study Arms	
Arm Title	Osivelotor (PF-07940367 or GBT021601)
Adults	Adult participants enrolling from C5351004 Part A and Part B will receive 150 mg maintenance dose. Dose adjustment and/or loading dose will be determined based on previous intervention/dose received in C5351004.
Adolescents and Pediatrics	Adolescent and pediatric participants from C5351004 Parts B and C will be administered a dose that provides generally equivalent exposure to adult participants.

**Duration of Treatment:** Participants may receive study drug for up to 252 days, as long as they continue to receive clinical benefit that outweighs risk as determined by the Investigator and/or until the participant has access to osivelotor from an alternative source (eg, through commercialization, a managed-access program, or a Sponsored initiative) or until the Sponsor decides to terminate the study.

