Preliminary data from these studies demonstrates that osivelotor has an acceptable safety and tolerability profile in healthy volunteers and participants with SCD as further described in Section 3.2. After single doses of osivelotor, blood and plasma PK and the mean % Hb occupancy of osivelotor increased in a linear manner following a single oral dose in healthy volunteers (Study GBT021601-011). In the initial part of the GBT021601-012 study of six SCD participants, after treatment at two dose levels, 50 mg for 5 weeks and 100 mg for 3

weeks, the % Hb occupancy averaged 32.6% (range 19.7% to 41.8%) and Hb levels increased by up to 3.1 g/dL (mean increase of 2.3 g/dL). Within the same timeframe, all participants demonstrated improvements in hematologic parameters, including reticulocytes and absolute reticulocytes, lactate dehydrogenase (LDH), and indirect bilirubin (Brown, Redfern et al. 2021).

GBT021601-013 is an ongoing Phase 1, single-center, open-label study to assess the mass balance, excretion, and PK of a single oral dose of [C]-osivelotor in healthy participants.

GBT021601-014 is an ongoing Phase 1, open-label, single-dose, non-randomized, parallel group study to evaluate the PK, safety, and tolerability of osivelotor in adult participants with renal impairment.

C5351004 is a three-part, multicenter, Phase 2/3 study of orally administered osivelotor in participants with SCD. Part A will evaluate the safety, tolerability, and efficacy of 12 weeks of osivelotor in adult participants with SCD, and determined the optimal dose of 150 mg for Part B. Part B will evaluate the efficacy of 150 mg osivelotor versus placebo in adult and adolescent participants with SCD for 48 weeks. Part C is a single-arm study which will evaluate the PK and safety of single and multiple doses of open-label osivelotor administered to pediatric participants. The study is ongoing.

Participants with SCD who participated in an osivelotor clinical study may be eligible to enroll in this open-label extension study (C5351005).

A detailed description of the chemistry, pharmacology, efficacy, and safety of osivelotor is provided in the PF-07940367 Investigator's Brochure (IB) (Pfizer, 2023), which is the Single Reference Safety Document (SRSD) for this study.

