## 5. STUDY DESIGN

### 5.1. Overall Design

This multicenter, global, open-label extension study is designed to assess the safety of long-term treatment with osivelotor in participants with SCD. The study will be conducted globally and will be available to eligible participants enrolled in a prior Pfizer-sponsored osivelotor clinical study (originating study). Participants must meet the entry criteria for this

study to be eligible for enrollment (see Section 6.1). The study will have a global distribution, and up to approximately 500 participants will be enrolled.

Eligible participants will receive osivelotor administered orally daily if they continue to receive clinical benefit that outweighs risk, as determined by the Investigator, until the participant has access to osivelotor from an alternative source (eg, through commercialization or a managed-access program).

Eligible participants will receive open-label osivelotor at Baseline (Day 1). It is intended that Day 1 coincides with the final visit from the originating osivelotor study. End of Treatment (EOT) assessments from the originating study will serve as Baseline assessments for this study. If Day 1 for this study is greater than 7 days from the completion of the originating study, new baseline assessments will be obtained. If during the period between Day 1 of this study and completion of the originating study no dose is received for greater than 3 consecutive days, an appropriate loading dose will be administered prior to continued maintenance dosing (see Section 11.3 for detail). Additional assessments that may not have been included in the prior EOT assessments are outlined in the Schedule of Assessments and will need to be completed prior to study drug administration.

Participants who participated in Part A of C5351004 or any other open label osivelotor study, will undergo safety and outcome assessments at Baseline (Day 1) and every 12 weeks thereafter (Table 2).

Participants from Part B of C5351004, or any other randomized, blinded, placebo controlled osivelotor study will undergo safety and outcome assessments at Baseline (Day 1), Week 8, Week 16, Week 24, and every 12 weeks thereafter (Table 3).

Pediatric participants from Part C of C5351004 will undergo safety and outcome assessments at Baseline (Day 1), Week 2, Week 4, Week 8, Week 12, Week 16, Week 20, Week 24, and every 12 weeks thereafter (Table 4).

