### **6.2. Secondary Endpoint(s)**

#### **6.2.1. Annualized rate of VOC**

The summary and analyses of on-treatment VOCs will include the following:

- Duration of on-treatment period (weeks)
- Total participant-years

- Total number of VOCs
- Total number of uncomplicated VOCs
- Total number of complicated VOCs and total for each type (ACS, hepatic sequestration, splenic sequestration, priapism)
- Number of participants with VOCs
- Number of VOCs per participant
- Number of uncomplicated VOCs per participant
- Number of complicated VOCs per participant
- Annualized incidence rate of VOC
- Annualized rate of VOC along with 95% CI (using Negative Binomial Model described below)

A listing of VOC data will be provided.

Multiple VOC events will be counted per participant. Both complicated and uncomplicated VOC events will be included for the calculation of the VOC rate.

**Annualized incidence rate of VOC on-treatment** will be calculated at the group level using the formula below:

$$\text{Annualized Incidence Rate of VOC on – treatment} = \frac{\text{sum of number of events on – treatment}}{\text{sum of participant years on – treatment}}$$

where participant years on-treatment for each participant = (EOT date – date of first dose of study drug+1)/365.25. EOT date is the last known treatment date from the EOT page in CRF.

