#### **Annualized rate of VOC on-treatment using Negative Binomial Model**

This analysis will not be performed by group but rather by combining all participants. A negative binomial model will be fitted to model the number of VOC events. The response variable is the number of VOC events for each participant. The independent variable is dose arm (100 mg, 150 mg) and the natural log of participant years (at participant level) will be used as the offset to account for the varying lengths of participant time on-treatment or on-study. The annualized rate and corresponding 95% CI will be presented for each dose arm and overall (100 mg + 150 mg).

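### A VOC recording limit of Week 48, apparently carried over from the parent study, conflicts with open-ended treatment and with the SAP's person-time; if sites applied it, the annualized VOC rate is too low

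*Protocol*

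**What the plan says.** **Recording limit.** Protocol 9.4.12.1.1 states: "All VOCs are to be recorded throughout the entire treatment period, up to Week 48". It then continues recording to a Week 60 follow-up visit "for participants who do not enroll in the OLE study".

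**Other VOC instructions, none with an end date.** Protocol 9.4.12.1 says of these events: "These events will be recorded on the VOC page in the participant's CRF within 72 hours". Protocol 9.2 has participants attend or notify the site about VOC visits, lists the annualized VOC rate among the efficacy assessments, and has outcome measures evaluated every 12 weeks after the first months. None of the four schedules of assessments has a VOC row.

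**Treatment duration.** Protocol 5.1 continues treatment, while benefit outweighs risk, "until the participant has access to osivelotor from an alternative source". The schedules show visits at day 252 and beyond. The synopsis, under Duration of Treatment, says: "Participants may receive study drug for up to 252 days".

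**Analysis.** SAP 6.2.1 divides on-treatment events by on-treatment participant-years, counted from first dose to EOT. It adds: "EOT date is the last known treatment date from the EOT page in CRF". The negative binomial model uses the log of participant-years as its offset "to account for the varying lengths of participant time on-treatment or on-study". SAP 2.1 says that all VOC data will be summarized. Nothing in the SAP cuts events or person-time at Week 48. SAP Tables 2 to 5 list analysis visits to target day 672 (Week 96) and continue every 12 weeks.

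**The concern.** The Week 48 and Week 60 limits do not fit this study. Everyone here has entered the OLE, so the Week 60 extension applies to nobody. No schedule has such a follow-up visit; the end-of-study visit is about 12 weeks after the last dose. The wording matches the parent study's Part B, which compares "150 mg osivelotor versus placebo in adult and adolescent participants with SCD for 48 weeks". According to SAP 2.2.3, only participants from Part A enrolled, and Protocol 3.1 gives Part A a 12-week treatment period. Week 48 therefore has no role in the design of this study.

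At stake is a mismatch between numerator and denominator. A site that follows the sentence literally stops entering VOCs at Week 48, while the SAP goes on counting time at risk until EOT. The error would run in one direction, downward, and would grow with treatment time. SAP 3.4 also tabulates an annualized VOC rate for the 12 months before parent-study screening. With no control arm, an artificial fall could be read as benefit. Adverse event data would not fill the gap, because Protocol 9.4.12.1 keeps ordinary VOCs off the AE and SAE pages unless the investigator judges them worse than expected or possibly drug-related.

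**Working it through.** The documents state no VOC rate, power or precision figure, so there is no plan figure to reproduce. The check applies the SAP formula to the literal recording rule.

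**Inputs**
- Events recorded to Week 48: 48 × 7 = 336 days (Protocol 9.4.12.1.1, read literally).
- Person-time: (EOT date − first dose date + 1)/365.25 years, not capped (SAP 6.2.1). Call the number of days T.
- True rate L per year: not given. Assumed constant, shown for 1 to 4 per year.
- Treatment lengths: not given. Shown for 36 to 96 weeks.

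**Formula**
- Expected recorded events = L × min(T, 336)/365.25.
- Person-years = T/365.25.
- Expected estimate ÷ true rate = min(T, 336)/T, which is min(1, 48/T) with T in weeks.

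**Results**

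| Treatment length | Days | Estimate ÷ true rate | Estimate if L = 1, 2, 3, 4 per year |
|---|---|---|---|
| 36 weeks (252-day figure) | 252 | 1.00 | 1.00, 2.00, 3.00, 4.00 |
| 48 weeks | 336 | 1.00 | 1.00, 2.00, 3.00, 4.00 |
| 60 weeks | 420 | 336/420 = 0.80 | 0.80, 1.60, 2.40, 3.20 |
| 72 weeks | 504 | 336/504 = 0.67 | 0.67, 1.33, 2.00, 2.67 |
| 84 weeks | 588 | 336/588 = 0.57 | 0.57, 1.14, 1.71, 2.29 |
| 96 weeks | 672 | 336/672 = 0.50 | 0.50, 1.00, 1.50, 2.00 |

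Where durations differ between participants, the pooled ratio is Σ min(Tᵢ, 336)/Σ Tᵢ. If half stop at 48 weeks and half at 96, it is (336 + 336)/(336 + 672) = 0.67.

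**Model check.** A negative binomial model with dose arm and log-years offset was fitted to simulated data (20,000 per arm, assumed true rate 3.0 per year, assumed dispersion 0.8).
- 84 weeks in both arms, events cut at Week 48 and time to EOT: 1.71 and 1.69 per year.
- Assumed 60 weeks in one arm and 96 in the other, same mismatch: 2.38 and 1.51 per year, a spurious rate ratio of 0.63. The formula gives 0.50/0.80 = 0.625.
- Events and time both to EOT, or both cut at Week 48: 2.96 to 3.01 per year in every case.

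**The offset wording.** The on-study alternative matters even with full capture. If on-treatment events were set against time to an EOS visit 84 days after the last dose, the ratio at T = 336 would be 336/(336 + 84) = 0.80.

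**The case against.** The strongest reply is that the sentence is recognizably parent-study text and that sites may well have ignored the limit. It opens by covering the whole treatment period, and its Week 60 clause describes people who cannot be in this study. Protocol 9.2 and 9.4.12.1 call for VOC notification, recording and review with no end date. This stands. A reader might infer that Section 9.4.12.1.1 is the only rule on VOC recording; it is not. It is the only place that states an end to recording, and it conflicts with the others.

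A reader might also infer that the reported rate is biased, or that it escapes bias only if everyone stops by Week 48. The documents support neither. Bias needs both treatment past Week 48 and sites that stopped recording then. Continued recording removes it whatever the treatment length.

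The size is also open. A 43% shortfall (1 − 0.57) is a worst case that assumes 84 weeks of treatment, a constant rate and no later capture. SAP visit windows are programming allowances, not observed follow-up. If the synopsis's 252 days governed, the bias would be zero.

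Finally, the SAP is largely sound here. It already sets on-treatment events against on-treatment years and has no Week 48 cut. The endpoint is one of three secondary endpoints, no hypothesis is tested, and no decision rule depends on it.

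What remains is a real contradiction about when a listed endpoint is recorded. If sites resolved it differently, under-counting would be uneven, and the SAP has no check that would reveal this.

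**Conclusion.** The recording sentence is wrong for this study and conflicts with Protocol 5.1, 9.2 and 9.4.12.1 and with SAP 6.2.1. This is an internal inconsistency with a conditional consequence. If sites applied the limit, the annualized VOC rate is too low for anyone treated beyond Week 48, by the factor min(1, 48/T): 0.80 at 60 weeks to 0.50 at 96. That range assumes a constant VOC rate and no capture after Week 48. Partial capture would give a smaller bias; continued recording, or treatment ending by Week 48, gives none. Actual treatment lengths and site practice are not documented, so no single figure can be attached to this trial. Type I error and power are not affected. The point still merits action before the primary analysis, because analysis cannot restore events that were never recorded.

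**What to change.** 1. **Protocol 9.4.12.1.1.** Replace the sentence with one stating that VOCs are recorded for every participant from Day 1 through the EOS/ET visit. Drop the Week 48 and Week 60 references.
2. **SAP 6.2.1.** Define an on-treatment VOC as one with onset from first dose to EOT. Use that same interval for the participant-years and the model offset, and delete the words *or on-study*. The onset rule is needed because recording to EOS will also collect events after the last dose.
3. **Site confirmation.** Ask sites whether VOCs after Week 48 were entered, and collect any that were missed.
4. **If capture was incomplete.** Report a rate with events and person-time both cut at Week 48 (day 336).
5. **Treatment duration.** The 252-day figure in the synopsis and the open-ended treatment in Protocol 5.1 contradict each other and must be reconciled.

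The cost is a few sentences of protocol or CRF guidance and SAP text, one round of site queries, and source documents and blinded adjudication (Protocol 9.4.12.1.2) for any newly found events. The last item could be the largest, since SAP 2.2.3 already describes enrollment in the past tense and the queries would be retrospective.

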#### **9.4.12.1.2. Source Document Collection for VOC Event Adjudication**

For each reported VOC, blinded source documentation to support the reported diagnosis will be submitted by the site to the VOC adjudication committee. Adjudication of all potential VOC events reported by the Investigator will be performed by a study Adjudication Committee – an independent, blinded panel comprised of experts in SCD. Responsibilities of the Adjudication Committee and definition of VOCs for adjudication will be provided in the Adjudication Committee Charter.

Source documents may include (but are not limited to) the following:

- Clinical notes (including history and physical examination [PE] findings),
- Emergency Department notes (including history and PE findings),
- Hospital discharge summary,

- Clinical laboratory values (eg, Hb concentration values for diagnoses of hepatic or splenic sequestration),
- Physical examination findings,
- Concomitant medications, and
- Chest X-ray (required for reporting an ACS).

Endpoints will be adjudicated by an independent endpoint adjudication committee. Any SAE that is adjudicated by the endpoint adjudication committee NOT to meet endpoint criteria is reported back to the investigator site of incidence. The investigator must report the SAE to Pfizer Safety within 24 hours of being made aware that the SAE did not meet endpoint criteria. The investigator's SAE awareness date is the date on which the investigator site of incidence receives the SAE back from the endpoint adjudication committee.

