#### **9.4.8. Serious Adverse Events, Serious Adverse Drug Reactions, and Requirements for Immediate Reporting**

All SAEs, regardless of causal attribution, must be reported by the Investigator/designee or site personnel within 24 hours of SAE awareness on the AE eCRF and reported to Pfizer Safety via PSSA. In the event that PSSA is not available, paper SAE report forms will be used to report the SAE and faxed or emailed to the Sponsor or CRO designee. The information reported on paper SAE report form should be entered into the EDC once available.

The Sponsor or designee may request additional source documentation pertaining to the SAE from the investigational site. Follow-up reports must be submitted within 24 hours of awareness and participant identifier information (eg, name, medical record number) must be redacted in the hospital discharge summaries, autopsy reports, and/or death certificates.

Follow-up SAE information must be submitted within 24 hours of awareness as additional information becomes available. All SAEs regardless of causal attribution must be followed to resolution or stabilization, or until reasonable attempts to determine resolution of the SAE are performed.

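### A non-serious event rejected by VOC adjudication has no stated route to the AE page, and the SAP does not say whether its VOC rate uses reported or confirmed events

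*Protocol*

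**What the plan says.** Protocol 9.4.12.1 separates VOCs from adverse events: "VOC events are not reported as an AE/SAE and must be reported on the VOC page". There are two exceptions. An event worse than expected for that participant, or one with a reasonable possibility of being drug-related, is reported as an SAE.

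Protocol 9.4.12.1.2 then requires adjudication without regard to seriousness: "Adjudication of all potential VOC events reported by the Investigator will be performed by a study Adjudication Committee". It adds "Endpoints will be adjudicated by an independent endpoint adjudication committee". For events the committee does not accept, the stated rule is "Any SAE that is adjudicated by the endpoint adjudication committee NOT to meet endpoint criteria is reported back to the investigator site of incidence", and the investigator then reports the SAE. Protocol 9.4.8 puts SAEs "within 24 hours of SAE awareness on the AE eCRF and reported to Pfizer Safety via PSSA". Further detail is deferred: "Responsibilities of the Adjudication Committee and definition of VOCs for adjudication will be provided in the Adjudication Committee Charter".

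SAP 6.1.1 identifies the types of TEAE from the AE CRF. The VOC page is not named as a source. SAP 6.2.1 describes the VOC count as "Multiple VOC events will be counted per participant" and "Both complicated and uncomplicated VOC events will be included for the calculation of the VOC rate". SAP 3.2.1 defines a VOC clinically. Neither section, nor the negative binomial model, mentions adjudication. SAP 2.1 lists the departures from the protocol's analysis plan, and dropping adjudication is not among them.

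**The concern.** Two results depend on where a rejected event ends up: the primary TEAE incidence and the secondary annualized VOC rate. The VOC definition admits events that need not be serious, for example an outpatient or urgent-care visit for pain with an increase in oral narcotics. If the committee attributes such an event to another cause, it is by that verdict an ordinary adverse event, which a long-term safety study is meant to capture. The site that recorded it as a VOC is not told of the rejection, so it has no reason to enter it as an AE.

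A second endpoint may also be touched. SAP 2.1 widens SCD-related SAEs to all SCD-related AEs, and the list in SAP 3.2.3 includes pneumonia and osteonecrosis. It is an inference, but a reasonable one, that these could be the alternative diagnosis for a rejected acute chest syndrome or pain crisis.

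On the VOC side, the study is open-label, so an independent verdict is a useful check on investigator classification. The SAP leaves open whether that verdict enters the analysis.

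**Working it through.** The documents give no VOC rate, rejection share or seriousness share, so there is no planned figure to reproduce. The main check follows an event through the stated rules.

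**Routing.** Take an event entered on the VOC page that meets neither exception in Protocol 9.4.12.1.

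| Event and verdict | VOC rate, if VOC-page events are counted | VOC rate, if confirmed events are counted | TEAE data (AE CRF) |
|---|---|---|---|
| Confirmed | counted | counted | no, by design |
| Rejected, serious | counted | not counted | yes, through the return rule and 9.4.8 |
| Rejected, non-serious | counted | not counted | no stated route |

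Three things follow:

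1. The bottom-right cell is the same whichever VOC source is used. The loss from TEAE data needs no assumed number.
2. If VOC-page events are counted, both kinds of rejected event inflate the VOC rate, and a rejected SAE with onset in the TEAE window appears as both a VOC and a TEAE. No rule removes or flags its VOC-page record.
3. If confirmed events are counted, a rejected non-serious event appears in neither endpoint.

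**Illustrative size.** Let r be the share of reported VOCs that are rejected and s the share of rejected events that are non-serious. Both are assumptions.

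- Reported-to-confirmed VOC rate ratio, same participant-years: 1/(1 - r).
  - r = 0.10: 1/0.90 = 1.11
  - r = 0.20: 1/0.80 = 1.25
  - wider range, r = 0.05 to 0.30: 1/0.95 = 1.05 to 1/0.70 = 1.43
- Events with no route to the AE page, per 100 reported VOCs: 100 × r × s.
  - r = 0.10, s = 0.50: 5
  - r = 0.20, s = 0.50: 10
  - wider range, r = 0.05 with s = 0.25 to r = 0.30 with s = 0.75: 1.25 to 22.5

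The rate ratio applies only if VOC-page events are counted. The second quantity applies under either source.

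**Unit.** The second quantity counts events. The overview table in SAP 6.1.1 reports both the number of TEAEs and the number of participants with TEAEs, while the system organ class and preferred-term tables count each participant once per term. A missing event changes participant-level incidence only if that participant has no other qualifying event. The effect there is smaller than on event counts.

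**The case against.** Three stronger readings are tempting, and the documents do not support them.

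- A reader might infer that the SAP counts rejected events as VOCs. It does not say so. It is silent on the source, the protocol says endpoints are adjudicated, and SAP 2.1 does not withdraw that. The SAP definition also excludes pain with another medically determined cause, so a rejected event would fail it if the verdict were applied. The sentence on counting several VOCs per participant concerns recurrent events, not the data source.
- A reader might infer that the verdict affects nothing. It does: a rejected serious event is reported as an SAE and so enters the AE data.
- A reader might infer that every VOC stays off the AE page. The two exceptions route the unexpectedly severe and the possibly drug-related events to SAE reporting, and these matter most for safety.

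Other points for the plan also carry weight. The Adjudication Committee Charter was not available and may already return non-serious events. The protocol sentence concerns SAE reporting and does not forbid a wider return. Reported VOCs remain visible in the SAP's VOC listing, and a data monitoring committee and safety review team follow them. The study has no comparator and tests no hypothesis.

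The general duty in Protocol 9.4.6.1 to record all AEs is the best answer to the gap, but it does not close it. A site that still believes the event was a VOC, and is not told otherwise, will properly leave it on the VOC page. The charter might settle the return path, but as the protocol describes its content it would not settle which count the SAP analyses.

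**Conclusion.** The point holds in two parts. First, under the stated rules a rejected non-serious event has no route to the AE page and is absent from the TEAE data. This follows from the text, subject only to what the charter may add. Second, the SAP leaves the source of the VOC count undefined although the protocol requires adjudicated endpoints, and the choice decides whether rejected events inflate the rate or drop out of both endpoints.

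The size cannot be known from the documents. The figures of 1.11-1.25 for the VOC rate, and of 5-10 missing events per 100 reported VOCs, illustrate assumed shares of 10-20% rejected with half non-serious. They are not estimates of bias in this study. The change is worth making because it affects the primary safety data and the adjudication it relies on is already planned.

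**What to change.** - **Protocol 9.4.12.1.2, or the charter if it does not already say so:** return every rejected event, serious or non-serious, to the site. The site enters it on the AE page with its original onset date, so that the TEAE window is applied correctly, and the VOC-page record is flagged as rejected. Keep the 24-hour reporting rule for SAEs.
- **SAP 6.2.1:** state that the main VOC analysis counts committee-confirmed events, consistent with the protocol, and give the investigator-reported count as a supporting row. Naming the source is the essential step. If the sponsor prefers investigator-reported events, SAP 2.1 should list that as a modification.
- **Before database lock:** query sites once for non-serious events already rejected, so that they reach the AE page.

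The cost is a small protocol or charter edit, a short SAP addition and the retrospective site queries. No new assessment of participants is needed, because the protocol already provides for adjudication.
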